women who are initially non-returners. Screening will be defined as: a) return of an HPV self-test and negative for a high-risk HPV infection; b) return of an HPV self-test, positive for a high-risk HPV infection, and attendance at a follow-up appointment; or c) receipt of a clinic-based test (e.g., Pap test). Hypothesis 1b: The increase in screening will be similar across patient characteristics.

Aim 2 (implementation outcomes): Assess the fidelity, sustainability, and cost-effectiveness of the intervention. Hypothesis 2a: We hypothesize that the intervention will be implemented with high fidelity and sustained by the clinics/health systems. Hypothesis 2b: We also hypothesize that the intervention will be a cost-effective strategy for increasing cervical cancer screening.

Aim 3 (client outcomes): Determine satisfaction with the intervention at the patient- and provider-levels. Hypothesis 3a: Women will report high levels of satisfaction with HPV self-testing (if HPV self-test is returned) and PN (if received). Hypothesis 3b: Healthcare providers will report high levels of satisfaction with the provider education sessions and have improved knowledge, attitudes, and beliefs about HPV self-testing.

[figure not shown]
3. Methods

Overview

We will examine the effectiveness and implementation of the multilevel intervention using a delayed intervention trial (Figure 1). The methodology for this study will draw heavily upon our recently completed pilot study of a mail-based HPV self-testing program (IRB# 2015C0036).²⁴ Further, this study will build upon the formative work currently being done for this P01 program under IRB# 2019C0169. The study described in this protocol will involve a Group Randomized Trial (GRT). In GRTs, identifiable groups are randomized to a treatment condition with measurements taken on members from those groups to assess the impact of the intervention. In this project, health systems will be randomized to one of two study arms (Group 1 will be the Early Intervention and Group 2 will be the Usual Care Continued/Delayed Intervention). Please note that similar to IRB# 2015C0036, the intervention will be referred to as “The HOME (Health Outcomes through Motivation and Education) Project” or simply as the “HOME Project”.

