The project's total sample size will be 1800 women across Years 2-5 (900 women from Group 1 clinics/health systems and 900 from Group 2 clinics/health systems). These sample sizes are feasible given the expected sampling frame size (see Table 1) and will give us at least 90% power for the below analyses.⁴³ The power calculation assumed a two-sided alpha=0.05, an intraclass correlation coefficient<0.017 (based on our pilot study), and the below outcome occurrences.

Primary Analyses

Primary analyses will examine the proportion of women from Year 2 screened, as defined above, and use an intent-to-treat approach. To compare treatment groups (Group 1 vs. Group 2), we will use generalized linear mixed models (GLMMs) to account for the correlation between women from the same clinic,⁴⁴ though we expect cluster effects to be low (i.e., intraclass correlation coefficient<0.017 based on our pilot study). Since our outcome is binary, we will use a logit link to estimate odds ratios for the GLMMs. We expect that 30% of women from Group 1 clinics/health systems and 10% of women in Group 2 clinics/health systems will be categorized as screened. The primary model will be unadjusted, but we will conduct sensitivity analysis that include potential confounders due to imbalance from randomization ($p<0.10$ when comparing groups). Results will determine the effectiveness of the intervention in increasing cervical cancer screening compared to usual care.

Secondary Analyses

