We will conduct several secondary analyses for Aim 1. First, we will examine the proportion of HPV self-test returners who returned their self-test following receipt of PN. Results will provide valuable data on the added benefit of PN on HPV self-test return. Second, we will use GLMMs with a logit link to examine potential differences in the proportion of women screened across project years within each treatment group (i.e., comparing Years 2, 3, 4, and 5 for Group 1). Results will determine how screening rates changed over time, which will be key in assessing whether the intervention was maintained during the Bundling and Sustainability phases. Third, to assess if the intervention was equitable, we will use GLMMs with a logit link to examine if patient characteristics are associated with women being categorized as "screened". Fourth, to assess safety, we will descriptively examine women's reports of any issues experienced when using their HPV self-test. Lastly, we will descriptively examine the prevalence of high-risk HPV infection, abnormal clinic-based cervical cancer screening tests, and cervical abnormalities among women.

Aim 2 (Implementation Outcomes)

Implementation outcomes will examine the fidelity, sustainability, and cost-effectiveness of the intervention. We hypothesize that the intervention will be implemented with high fidelity and sustained by the clinics/health systems (Hypothesis 2a). We also hypothesize that the intervention will be a cost-effective strategy for increasing cervical cancer screening (Hypothesis 2b).

Fidelity

We will use several strategies to ensure and examine fidelity (i.e., the degree to which the intervention is conducted according to protocol). At the patient-level, we will develop an electronic tracking system to track all mailings (e.g., self-test distribution) and other data collection activities. At the provider level, we will conduct the provider education sessions using a standardized PowerPoint presentation. Data during the sessions will be collected using a checklist (for project team use only) that includes key observations related to fidelity (e.g. the presence of participants during entire session).

Sustainability

We will examine the screening rates during the Sustainability phase(s) for both Groups 1 and 2 to determine sustainability.

Cost-effectiveness

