Cost-effectiveness analyses will be conducted from a payer perspective. We will first conduct a cost identification analysis. We will carefully consider all costs of the intervention, including those for HPV self-test devices, PN training/implementation, staff, mailing costs, and administrative costs. We will value the costs of each item using standard costs, and we will carefully distinguish costs related to scientific research from those of the interventions themselves. We will only include the intervention costs in our cost-effectiveness analyses. We will then aggregate the measures of costs and intervention effectiveness and calculate incremental cost-effectiveness ratios (ICER). The ICER measures the cost at which an added unit of outcome can be achieved by the intervention. Thus, the ICER will represent the marginal cost of an additional patient screened for cervical cancer due to the intervention. We will also conduct sensitivity analyses.

Aim 3 (Client Outcomes)

For client outcomes, we will determine the satisfaction with the multilevel intervention at the patient- and provider-levels (Table 2).

Table 2. Client Outcomes and Data Sources

Outcome	Measure	Level	Data Source
Satisfaction	Satisfaction with HPV self-testing and PN	Patient-level	Patient satisfaction survey
Satisfaction	Satisfaction with provider education sessions and change in knowledge, attitudes, and beliefs	Provider-level	Surveys from provider education sessions

Patient-Level

We hypothesize that women will report high levels of satisfaction with HPV self-testing (if HPV self-test is returned) and PN (if received) (Hypothesis 3a). Patient-level satisfaction data will come from the patient satisfaction surveys sent to women. We will examine satisfaction with both the HPV self-test device (appearance, usability, return process, etc.) and its instructions (appearance, readability, etc.). We will use items based on those from our pilot study to assess these constructs.²⁴ For women who received PN, we will also assess their satisfaction with PN using items from our past PN research.³⁴ All satisfaction items will use 5-point Likert response scales. We will consider means of 4.0 and greater to indicate high levels of satisfaction. We expect about 80% of women who were sent an HPV self-test to return a completed patient satisfaction survey (based on mailed survey return in our pilot study²⁴).

Provider-Level

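### Hypothesis 2a says the intervention will be sustained, but the plan gives no criterion for it, and a test for differences between years cannot supply one with 100 women per group-year

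*Combined protocol and SAP*

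**What the plan says.** Under Specific Aims, Aim 2, the sponsor writes: "We hypothesize that the intervention will be implemented with high fidelity and sustained by the clinics/health systems". Two places in Statistical Methods bear on the second half of that hypothesis.

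- Aim 1, Secondary Analyses: logit mixed models will "examine potential differences in the proportion of women screened across project years within each treatment group". The results are to show the trend in screening, "which will be key in assessing whether the intervention was maintained during the Bundling and Sustainability phases".
- Aim 2, Sustainability, in full: "We will examine the screening rates during the Sustainability phase(s) for both Groups 1 and 2 to determine sustainability".

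Neither gives a margin, a minimum rate, a confidence-interval rule or a definition of sustained. The plan does set a threshold elsewhere. For patient satisfaction it states: "We will consider means of 4.0 and greater to indicate high levels of satisfaction".

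Group 1 has 600 women in Year 2. From Year 3 on, each group contributes 100 women a year. Group 1 is in the Sustainability phase in Years 4 and 5, and Group 2 in Year 5 only. Group 2's active delivery is Year 3, because its Year 2 is usual care.

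**The concern.** Sustained means that no important part of the benefit was lost. A test for differences between years takes no change as its null hypothesis, so failing to reject it is not evidence of maintenance. The fewer women there are in the later years, the more likely that failure becomes, and the later years are the small ones.

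No usual-care group runs alongside after Year 2, so comparison across years carries the whole maintenance conclusion. As written, Hypothesis 2a has no stated result that would count against it. A real loss of benefit could be reported as sustained without departing from the plan.

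**Working it through.** **Inputs from the documents.** Expected screening of 30% (Group 1) and 10% (Group 2) in Year 2, from Primary Analyses. Two-sided alpha of 0.05 and an intraclass correlation below 0.017, from Sample Size. Five health systems per group, from Randomization. Yearly sample sizes from the Year 2 to Year 5 sections.

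**Assumptions.** Screening is 30% under active delivery in both groups and falls to 20%, which is half the planned 20-point effect. Usual care would have stayed at 10%. Women sampled in different years are independent apart from a shared system effect. Women are spread evenly over systems.

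**1. The plan's own figure.** The plan says the sample "will give us at least 90% power for the below analyses". For the primary comparison:

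- Design effect = 1 + (120 − 1) × 0.017 = 3.023, so the effective n is 600/3.023 = 198.5 per group.
- SE under the null = √(0.20 × 0.80 × 2/198.5) = 0.0402. SE under the alternative = √((0.21 + 0.09)/198.5) = 0.0389.
- Power = Φ((0.20 − 1.96 × 0.0402)/0.0389) = Φ(3.12) = 99.9%, or 98.1% using a t distribution on 5 df.

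The figure holds for the primary analysis.

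**2. Two-period contrasts, 30% against 20%, no design effect.**

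Logit model: log odds ratio = ln(0.30/0.70) − ln(0.20/0.80) = 0.539; SE = √(1/(0.21 n₁) + 1/(0.16 n₂)); power = Φ(0.539/SE − 1.96).

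Pooled test of proportions: power = Φ((0.10 − 1.96 × SE₀)/SE₁), with SE₀ from the pooled proportion and SE₁ unpooled.

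| Contrast | n | Logit SE | Power, logit | SE₀ / SE₁ | Power, pooled | Chance of non-significance |
|---|---|---|---|---|---|---|
| Group 1, Year 2 vs Year 5 | 600 vs 100 | 0.265 | 53% | 0.0488 / 0.0442 | 54% | 46-47% |
| Group 1, Year 2 vs Years 4-5 | 600 vs 200 | 0.198 | 78% | 0.0365 / 0.0339 | 80% | 20-22% |
| Group 2, Year 3 vs Year 5 | 100 vs 100 | 0.332 | 37% | 0.0612 / 0.0608 | 37% | 63% |

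If system-by-year variation were as large as an intraclass correlation of 0.017, power would fall to about 38% in the first row and 29% in the last.

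**3. Group 1 four-year test (3 df).** Noncentrality = Σ n(p − p̄)²/(p̄(1 − p̄)).

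- Years 4 and 5 both fall (30, 30, 20, 20%): p̄ = 0.278, noncentrality 7.75, power 64%. A simulated likelihood-ratio test gives 67%, so the chance of non-significance is about 33% (36% by the approximation).
- Only Year 5 falls (30, 30, 30, 20%): p̄ = 0.289, noncentrality 4.33, power 39%. Simulation gives 41%, so the chance is about 59% (61% by the approximation).

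For Group 2, a test over Years 2-5 would be significant because the intervention started (power above 99.9% under 10, 30, 30, 20%). It says nothing about maintenance.

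**4. What an estimate could deliver.** Take no true loss (30% throughout) and an illustrative 10-point margin. Combine the within-group contrasts by inverse variance.

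- No design effect: V₁ = 0.21 × (1/600 + 1/200) = 0.0014; V₂ = 0.21 × (2/100) = 0.0042; V = 1/(1/V₁ + 1/V₂) = 0.00105; SE = 0.0324. The half-width is 1.96 × 0.0324 = 6.4 points. The chance of excluding a 10-point loss is Φ(0.10/0.0324 − 1.96) = 87%.
- System-by-year variation equal to 0.017: the design effect is 3.023 at 120 women per system-year and 1 + 19 × 0.017 = 1.323 at 20. V₁ = 0.21 × (3.023/600 + 1.323/200) = 0.00245; V₂ = 0.21 × 2 × 1.323/100 = 0.00556; SE = 0.0412. The half-width is 8.1 points and the chance is 68%.

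**5. Why not pool crudely.** Group 1 makes up 600 of the 700 active-delivery women but 200 of the 300 Sustainability women. If true rates were 35% in Group 1 and 25% in Group 2 with no loss, crude rates would be (600 × 0.35 + 100 × 0.25)/700 = 33.6% and (200 × 0.35 + 100 × 0.25)/300 = 31.7%, a spurious drop of 1.9 points.

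**The case against.** A reader might infer that the plan will declare the intervention maintained whenever the year effect is non-significant. The documents do not say so. They state no such rule and no p-value threshold for this analysis. A logit mixed model yields estimates as well as tests, and Aim 2 looks at the Sustainability-phase rates directly. That stands, and the point is limited to the absence of a criterion. Examining rates without a threshold does not supply one.

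Sustained can also be read otherwise than as no important loss against active delivery. The Year 4 text is about clinics running the intervention themselves, and a 20% rate would still be twice the planned usual-care rate. That is fair: the half-effect benchmark is this review's illustration, not the sponsor's. It is also a reason for the sponsor to say which meaning is intended.

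The chance of missing a loss depends heavily on the contrast, and the one aligned with Group 1's Sustainability phase (Years 4-5 pooled) performs best, at 20-22%. The plan does not name that contrast, and Group 2 has nothing comparable.

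The remedy has a weakness of its own. From Year 4 women must return a completed eligibility form, whereas in the Year 2 procedure, which Year 3 mirrors, a woman who did not reply counted as eligible. Every Sustainability cohort falls after that change and both active-delivery cohorts fall before it. Women who return a form are plausibly more likely to return a kit, which could hide a loss. This objection stands in full, and the fix has to deal with it.

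Finally, this is a secondary and implementation outcome. The randomised Year 2 comparison is untouched.

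**Conclusion.** The concern holds in this form: a named hypothesis has no criterion, and the only model offered for it cannot by itself support a no-important-loss conclusion. For an assumed fall from 30% to 20%, and without a design effect, the chance of a non-significant result ranges from about 20% to about 63% across the contrasts the plan leaves open. System-by-year variation would raise it.

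These figures rest on 30% under active delivery in both groups and an unchanged 10% under usual care, neither of which the documents give beyond Year 2. The documents also do not support reading the 90% power statement as refuted. It is reproduced for the primary comparison, and no rates are given for the year comparisons. What can be said is that none of the Group 1 contrasts, and not the Group 2 Year 3 against Year 5 contrast, reaches 90% for a 10-point loss. The change should be made, but it does not bear on the primary result.

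**What to change.** In Aim 1, Secondary Analyses, with a cross-reference from Aim 2, Sustainability:

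- Base the maintenance conclusion on the estimated Sustainability-minus-active-delivery difference in the proportion screened, with a 95% confidence interval that allows for clustering.
- Form it within each group: Group 1 Years 4-5 against Year 2, and Group 2 Year 5 against Year 3. Combine the two by stratification, not by crude pooling, and also show each year.
- Conclude that the intervention was sustained only if the interval excludes a loss larger than a margin that the sponsor fixes before the Sustainability data are analysed. The 10 points used here is only an illustration.
- Report a non-significant year term alone as inconclusive.
- State that the contrast is confounded with the Year 4 change in eligibility confirmation, and do not conclude that the intervention was sustained without addressing that selection.

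The cost is plan wording and one further contrast from a model already planned, with no extra women. The downside is that some results will be reported as inconclusive. Even with no true loss and the illustrative margin, that would happen about 13% of the time without a design effect (100 − 87) and about 32% with system-by-year variation at 0.017 (100 − 68).

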Group 1 clinics/health systems will continue with the Sustainability phase, as described above during Year 5. Group 2 clinics/health systems will also enter the Sustainability phase, as described above, during Year 5. In this phase, 100 women across Group 1 health systems and 100 women across Group 2 health systems who remain unscreened/underscreened will be randomly sampled from the sampling frame and sent an HPV self-test.

Data Collection for Year 5

Data collection activities (Medical Record Review and Patient Satisfaction Survey) will be identical to those described for Year 3.

Statistical Methods: Analyses and Evaluation

We will conduct analyses/evaluation of each outcome type recommended for implementation research:³² implementation, service, and client outcomes.

Aim 1 (Service Outcomes)

Service outcomes will include intervention effectiveness, equitableness, and safety (Table 1). We hypothesize the intervention will increase cervical cancer screening and that PN will increase HPV self-test return among women who do not initially return their self-test (Hypothesis 1a). We think PN will increase HPV self-test return among these initial non-returners given PN's positive effect on health outcomes in past studies.²⁶⁻²⁹ Lastly, we hypothesize the increase in screening will be similar across patient characteristics (i.e., equitableness)(Hypothesis 1b).

Table 1. Service Outcomes and Data Sources

Outcome	Measure	Level	Data Source
Effectiveness	Cervical cancer screening	Patient-level	HPV self-test data and medical records
Equitableness	Demographic and health-related characteristics	Patient-level	Medical records
Safety	Reported issues in using an HPV self-test	Patient-level	Patient satisfaction surveys

Measures

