The patient-level effectiveness outcome and primary outcome for our project will be whether or not women get "screened" during the project. There are three ways a woman can be considered "screened." The first is to return their HPV self-test and test negative for high-risk HPV types. The second is to return their HPV self-test, test positive for high-risk HPV types, and then attend a follow-up appointment at their health system. We are requiring these women to attend a follow-up appointment to be considered "screened" given their HPV infection. The third way is to receive a clinic-based screening test (e.g., Pap test), regardless of HPV self-test return status. This will most likely apply to women in Group 2 health systems during the Usual Care Continued phase, but past studies have shown that some women will get a Pap test after receiving an HPV self-test in the mail (without using the self-test).⁴² All women not meeting one of these three criteria will be considered "unscreened." To determine this outcome, we will examine HPV self-test return status, HPV testing results, and EHR data (follow-up appointment attendance, Pap testing, etc.) for each sampled woman.

Among women who return their HPV self-test, we will examine the timing of device return and categorize each as returned within two weeks of distribution (i.e., prior to any PN) or after two weeks of distribution (i.e., following PN). We will also examine HPV testing results (positive or negative for high-risk HPV types) and collect data from EHR on the number of normal and abnormal clinic-based cervical cancer screening tests received by each woman and any cervical abnormalities found (i.e., low-grade squamous intraepithelial lesion, etc.).

To assess if the intervention is equitable (Figure 4), we will examine patient characteristics via data from HER (e.g., age and when their most recent clinic-based cervical cancer screening test prior to project entry occurred [if

ever]). Lastly, to assess safety, we will examine data from the patient satisfaction survey to see if women report any issues about using their HPV self-test. We do not anticipate such reports to be common, as HPV self-test devices have been used safely and easily by women in several research studies.⁶⁻¹⁵

Sample Size

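### Hypothesis 1b concerns whether the intervention's effect is similar across patient characteristics, but the only planned equity analysis asks who gets screened

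*Combined protocol and SAP*

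**What the plan says.** Under Specific Aims, Aim 1 carries this hypothesis: "Hypothesis 1b: The increase in screening will be similar across patient characteristics". The Aim 1 (Service Outcomes) section repeats it and makes it the meaning of equitableness: "we hypothesize the increase in screening will be similar across patient characteristics (i.e., equitableness)(Hypothesis 1b". Table 1 lists equitableness as one of three service outcomes.

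Primary Analyses compares Group 1 with Group 2 in Year 2 using a logit mixed model, and says what an increase is measured against: "Results will determine the effectiveness of the intervention in increasing cervical cancer screening compared to usual care". The effect scale is also given there: "Since our outcome is binary, we will use a logit link to estimate odds ratios for the GLMMs".

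Measures names the data for the equity question, with age and time since the last clinic-based test as examples: "To assess if the intervention is equitable (Figure 4), we will examine patient characteristics via data from HER" (sic, for EHR).

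The analysis itself is one sentence in Secondary Analyses: "Third, to assess if the intervention was equitable, we will use GLMMs with a logit link to examine if patient characteristics are associated" with a woman being classed as screened. It does not say which arms or project years enter the model. No section states an arm-by-characteristic interaction, an effect within subgroups, or a criterion for similar. The sensitivity analysis in Primary Analyses adds imbalanced confounders, which is adjustment and not effect modification.

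**The concern.** The hypothesis is about a difference of differences: does the gap between intervention and usual care change with, say, age? The planned model asks whether age predicts being screened. These are different quantities, and one cannot be recovered from the other.

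- If both arms are pooled, or arm enters only as a main effect, the coefficient for the characteristic averages over arms.
- If only Group 1 is used, the coefficient mixes the screening that would have happened under usual care (about 10% overall by the plan's assumption) with the effect of the intervention.

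Followed as written, the analysis could miss a large difference in effect, or flag a difference in background uptake that the intervention did not cause. The report could then call the intervention equitable or inequitable without having estimated its effect in any subgroup.

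**Working it through.** **Inputs from the documents.** Year 2 has 600 women per group. There are five health systems per group, so 120 women per system if sizes are equal. Expected screening is 30% in Group 1 and 10% in Group 2, two-sided alpha is 0.05, and the ICC is below 0.017 (0.017 used).

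**Inputs assumed.** The documents give no subgroup rates. I take a binary characteristic split 50/50 that varies within health systems, giving 300 women in each of four cells.

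**The plan's own power figure.** The design effect is 1 + (120 − 1) × 0.017 = 3.023, so the effective size is 600 / 3.023 = 198 per group. For 30% versus 10%, power is 99.9% by normal approximation and 99.4% with a t reference on 8 df. The stated minimum of 90% is met, but this covers only the overall comparison.

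**Formula for the interaction.** The difference in log odds ratios has SE = sqrt(Σ 1/(n·p·(1 − p))) over the four cells. Because the characteristic varies within systems, the cluster effect largely cancels: with 10% and 30% in both subgroups, simulated SEs were 0.323 with five clusters of 120 per arm and 0.326 with no clustering.

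**Three illustrations.** Rates run from usual care to intervention.

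| | Subgroup A | Subgroup B | Odds ratios A, B | What the association sees |
|---|---|---|---|---|
| 1 | 5% → 35% | 15% → 25% | 10.2, 1.9 | pooled: 20% vs 20% |
| 2 | 5% → 30% | 15% → 30% | 8.1, 2.4 | Group 1: 30% vs 30% |
| 3 | 15% → 40.5% | 6% → 19.8% | 3.86, 3.86 | Group 1: 40.5% vs 19.8% |

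Arm totals are 10% and 30% in 1 and 2, and 10.5% and 30.1% in 3. The common odds ratio in 3 is (0.30/0.70)/(0.10/0.90) = 3.857.

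- *Illustration 1.* ln(10.23) − ln(1.889) = 1.689; SE 0.359; z = 4.71. A Group 1-only association (35% vs 25%) has z = 2.66 and power 0.76.
- *Illustration 2.* ln(8.143) − ln(2.429) = 1.210; SE 0.358; z = 3.38; power 0.92. The Group 1 association is exactly nil.
- *Illustration 3.* The interaction is zero. Pooled rates are 27.75% vs 12.88% (z = 6.3); Group 1 alone gives z = 5.4.

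**Simulated rejection rates.** Logit mixed models were fitted to five systems of 120 women per arm at ICC 0.017, with a likelihood-ratio test at 0.05. There were 1,000 runs for each interaction entry and 400 to 600 for each association entry.

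| | Association, arm as main effect | Association, Group 1 only | Interaction |
|---|---|---|---|
| 1 | 5.8% | 73.8% | 100% |
| 2 | not run | 4.5% | 92.8% |
| 3 | 100% | 100% | 4.6% |

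**Precision of the right analysis.** With 10% and 30% in both subgroups, SE = 0.325, so the 95% interval for the ratio of odds ratios is exp(±1.96 × 0.325) = 0.53 to 1.89. For an 80/20 split (480 and 120 per arm), SE = 0.407 and the interval is 0.45 to 2.22. For 10% → 35% versus 10% → 25%, ln(4.846) − ln(3.0) = 0.480, SE 0.326, z = 1.47 and power 0.31 (34.1% in the simulated models).

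**The case against.** **Increase could mean from entry.** Every sampled woman is unscreened when she enters, so the proportion screened in Group 1 is itself an increase from baseline, and a Group 1 association would address it. That reading is possible. But the plan does not limit the equity model to Group 1, and its effectiveness statement measures the increase against usual care, under which 10% are expected to be screened anyway.

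**An interaction is not ruled out.** This is true: one brief sentence does not exclude it. But a named hypothesis should not rest on a term that the plan nowhere states.

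**The scale matters, and increase may suggest percentage points.** This stands as a caution. Equal 20-point gains (5% → 25% and 15% → 35%) give odds ratios of 6.3 and 3.1, and the logit interaction would reject in about 53% of trials. In illustration 3 the gains are 25.5 and 13.8 points, and a risk-difference interaction would reject in about 76%. For the modest example above, power is 31% on the logit scale and about 61% on risk differences. The plan's stated scale is the odds ratio, so both need to be shown.

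**The illustrations are chosen.** Fair: 1 needs rates that cross over and 2 needs exact equality in Group 1. They show that the analysis can fail in either direction, not how often it will.

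**The interaction may not settle similarity either.** Also true for modest differences. Limited precision is a reason to report estimates with intervals, not to test a different quantity.

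**Conclusion.** The concern holds. Hypothesis 1b and its only analysis address different quantities, and the plan states no interaction or subgroup effect that would connect them. Under assumed but admissible rates, the planned association can sit at chance level (about 5% rejection) while subgroup odds ratios differ by a factor of 5.4 (10.23 / 1.889) or 3.4 (8.143 / 2.429). It can also reject in every run when the odds ratios are identical. Those sizes rest on assumed subgroup rates, an even split within systems and equal cluster sizes. The mismatch itself does not depend on them. One secondary hypothesis is affected; the primary comparison, its power and trial conduct are not. It should be fixed before the equity analysis is run.

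**What to change.** For each characteristic already to be collected, add the characteristic and its interaction with arm to the Year 2 Group 1 versus Group 2 logit mixed model.

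- Report the arm effect within each level and the ratio of odds ratios, each with a 95% interval, on the plan's odds-ratio scale. Give risk differences as supportive results and say so in advance, because the two scales can disagree.
- State that a non-significant interaction will not be read as similarity.
- Keep the association model as a description of who gets screened, and state which arms and years it uses.

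The cost is small. No new data are needed, and a binary or linear characteristic adds two terms to an existing model; a categorical one, such as time since last test with a never-tested level, adds more. The drawback is wide intervals, so modest differences may stay unresolved and must be reported that way. A characteristic that is constant within a health system, or an effect that varies between systems, would widen the intervals beyond those shown above.
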